## 9.0 DATA SUBMISSION SCHEDULE

Case report forms with appropriate source documentation will be completed according to the schedule listed in this section.

Case Report Form	Submission Schedule
Original Consent Form	Prior to registration
On-Study Form Medical History Form	Prior to starting treatment
Specimen Collection Form	Screening, immediately after radiotherapy completion (Fraction 5), 14 days after radiotherapy, and 30 days after radiotherapy
Questionnaires	Baseline, after radiation at 2 weeks, 1 month, 3 months, 6 months, and 1 year
Toxicity Form	Continuous
Treatment Summary Form	Completion of treatment
RECIST Form	Baseline, then 3 months, 6 months, and 1 year post treatment
Follow Up Form	After radiation at 2 weeks, 1 month, 3 months, 6 months, and 1 year
Death Form	At time of death (if applicable)

### 9.1 Adverse Event Collection in the Case Report Forms

All adverse events that occur beginning with start of treatment (minus exceptions defined in Section 7.0) must be captured in the Toxicity Form. Baseline AEs should be captured on the Medical History Form.

Participant death due to disease progression should be reported on the Toxicity Form as grade 5 disease progression. If death is due to an AE (e.g. cardiac disorders: cardiac arrest), report as a grade 5 event under that AE. Participant death must also be recorded on the Death Form.

## **10.0 DATA AND SAFETY MONITORING**

In compliance with the Washington University Institutional Data and Safety Monitoring Plan, the Principal Investigator will provide a Data and Safety Monitoring (DSM) report to the Washington University Quality Assurance and Safety Monitoring Committee (QASMC) semi-annually beginning six months after accrual has opened (if at least one patient has been enrolled) or one year after accrual has opened (if no patients have been enrolled at the six-month mark).

The Principal Investigator will review all patient data at least every six months, and provide a semi-annual report to the QASMC. This report will include:

- HRPO protocol number, protocol title, Principal Investigator name, data coordinator name, regulatory coordinator name, and statistician
- Date of initial HRPO approval, date of most recent consent HRPO approval/revision, date of HRPO expiration, date of most recent QA audit, study status, and phase of study
- History of study including summary of substantive amendments; summary of accrual suspensions including start/stop dates and reason; and summary of protocol exceptions, error, or breach of confidentiality including start/stop dates and reason
- Study-wide target accrual
- Protocol activation date
- Average rate of accrual observed in year 1, year 2, and subsequent years
- Expected accrual end date
- Objectives of protocol with supporting data and list the number of participants who have met each objective
- Measures of efficacy (phase I studies only if efficacy is objective of the protocol)
- Measures of efficacy
- Early stopping rules with supporting data and list the number of participants who have met the early stopping rules
- Summary of toxicities
- Abstract submissions/publications
- Summary of any recent literature that may affect the safety or ethics of the study

The study principal investigator and Research Patient Coordinator will monitor for serious toxicities on an ongoing basis. Once the principal investigator or Research Patient Coordinator becomes aware of an adverse event, the AE will be reported to the HRPO and QASMC according to institutional guidelines.

## 11.0 STATISTICAL CONSIDERATIONS

### 11.1 Study Design

This is a single arm study where 67 eligible patients with non-hematologic malignancies patients with large tumors ( $\geq 4.5$  cm) will undergo radiotherapy using Lattice SBRT. Lattice SBRT will be prescribed to 20 Gy in 5 fractions delivered every other day with a LATTICE simultaneous integrated boost (SIB) to 66.7 Gy in 5 fractions. Patients will be followed for 12 months after the completion of radiotherapy for treatment effect and treatment-related toxicity assessment. An exploratory study will analyze blood-based markers of treatment response, so blood will be drawn prior to and after completion of radiotherapy.

### 11.2 Study Endpoints

The co-primary endpoints are rate of local control of the treated (i.e. target) lesion at 6 months, and proportion of patients with treatment related grade 3+ CTCAE v5.0 toxicity. Local control will be determined by RECIST 1.1 analysis of baseline compared with imaging at 6 months. Imaging may include CT scan, PET/CT, or MRI. It is strongly suggested that the same imaging modality is used between baseline and at every follow-up timepoint for staging of disease.

Importantly, there are limited available data to determine expected local control of large tumors after SBRT. Almost all studies have focused on tumors with average maximal diameter of only 5.5 cm corresponding to a tumor volume of approximately 87 cc. In such studies, local control rates are approximately 70-85%. In the pilot study of Lattice SBRT at Washington University, the median treated tumor volume was 435 cc (N=14). Likewise, these few studies of SBRT for large tumors report a grade 3+ toxicity rate of 5-25%, varying based on tumor location.

Due to the lack of a reliable historical comparison, the enrollment target was defined by clinical considerations as opposed to power calculations for comparison with a historical control. This study instead seeks to establish the expected local control rate at 6 months for patients with such large tumors treated with Lattice SBRT. After discussing with internal and external stakeholders, we determined that a clinically reasonable bound on local control at 6 months would be 15%. Approximately 47 patients would be required to determine local control with a 95% confidence interval of +/- 15%; 67 patients will be enrolled to get 47 evaluable patients. We anticipate that up to 30% of patients may not be evaluable for local control at 6 months and are accounting for this potential drop-out rate by enrolling 67 patients. This is because patients with very large tumors needing palliative radiotherapy often have short survival.

Likewise, the study seeks to establish the expected grade 3+ treatment related toxicity rate for treatment of large tumors with lattice SBRT. The treatment will be considered safe if the grade 3+ treatment related toxicity rate is less than 20%, which is in line with prior studies of SBRT of large tumors.

As secondary endpoints, this study will evaluate patient reported outcomes through 12 months follow up. Comparisons of patient-reported outcomes such as pain in patients undergoing palliative radiotherapy are notoriously difficult. These can be impacted by the initial indication for palliative radiation (i.e. oligoprogression versus uncontrolled symptom), presence or absence of other tumors outside the target(s), subsequent therapies after treatment, and co-morbidities. This study will attempt to reduce this heterogeneity by studying the secondary endpoints within pre-specified subgroups. Additionally, this study will evaluate PROs using the reliable change index, which allows evaluation of the change of individual patient PROs of comparison to their own baseline.

The RCI utilizes the known retest reliability and standard deviation of a test to calculate the standard error of measurement and standard error of the difference between scores [Jacobson, 1992]. This value represents the level of change associated with statistically significant change from baseline. RCI is calculated as follows:

$$RCI = \frac{x_2 - x_1}{S_{diff}}$$

Where  $x_2 - x_1$  represents an individual's change between timepoints. This can also be reported as a difference in population mean.  $S_{diff}$ , the standard error of the difference between the two scores accounting for reliability of the test, is calculated as:

$$S_{diff} = \sqrt{2(S_E)^2}$$

$$S_E = s_1 \sqrt{1 - r_{xx}}$$

Where  $S_E$  is the standard error of measurement of the test,  $s_1$  is the standard deviation of the test results at the initial time point, and  $r_{xx}$  is the test-retest reliability of the measure. The test-retest reliabilities of PROMIS domains used in this study have been previously evaluated in patients with musculoskeletal conditions and range from 0.85-0.92 [Deyo, 2016].

The RCI will be calculated for each individual patient for pain score, PRO-CTCAE, and each PROMIS domain between baseline and the 3, 6, and 12 month time points. In order for a change to be deemed statistically reliable at a 90% confidence interval, the Z-score of the RCI must be greater than 1.645. The 90% confidence interval is standard use in the literature when calculating RCI because it increases the sensitivity in detecting reliable change and defines a change which occurs in only 5% of healthy individuals in either direction [Stein, Gray, Schmitt, Hensel]. Changes that exceed this threshold in either direction are likely due to actual change rather than due to chance. Individual changes are reported as either significant increase, significant decrease, or no change.

Mean RCI for each time-point and domain will be calculated to determine significant change on a population level for each sub-group. The  $S_{diff}$  for each domain will be used to calculate a minimum important change at each time-point based on a 90% confidence interval. Lastly, the proportion of individuals in each histology cohort group whose RCI indicated significant increase, significant decrease, or no change in PRO scores will be reported.

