## 2.0 OBJECTIVES AND ENDPOINTS

Objectives	Endpoints	Justification for Endpoints
Primary		
To evaluate the efficacy of 5-fraction palliative Lattice SBRT in patients with large lesions who are planning to undergo palliative radiotherapy ( $\geq 4.5$ cm).	Rate of target lesion local control at 6 months per RECIST 1.1	RECIST 1.1 is a standard measure of local control.
To evaluate the acute and sub-acute toxicity of 5-fraction palliative Lattice SBRT in patients with large lesions who are planning to undergo palliative radiotherapy ( $\geq 4.5$ cm).	Rate treatment-related, non-hematologic CTCAE v5.0 Grade $\geq 3$ toxicity at 6 months	SBRT to large tumors is traditionally associated with high dose to OARs, with sequelae of radiation-induced toxicities. As these patients have no effective treatment options, evaluation of the safety of this method of dose-

		escalation with SBRT is warranted. CTCAE v5.0 is a widely accepted standardized measure of treatment-related toxicity.
Secondary		
To assess pain response to Lattice SBRT	For patients that have pain, their pain level will be assessed with the pain Numeric Rating Scale (NRS)	The NRS is an 11-point scale for patient self-reporting of pain. This is selected because it is a reliable and clinically meaningful measure of pain that is extensively used in research and clinical practice.
To assess patient-reported toxicity outcomes	For patients that do not have pain, patient-reported symptom response will be assessed with PRO-CTCAE. A treatment site specific package of PRO-CTCAE measures will be defined for each treatment location (thorax, abdomen, pelvis, extremity)	PRO-CTCAE is a standardized inventory to collected patient reported symptomatic adverse events in clinical trials.
To assess patient reported quality of life outcomes	Patient reported quality of life and functional outcomes will be measured before treatment, after treatment, and at each follow up with the PROMIS Global, Physical Function, Pain Interference, Anxiety, and Depression system	This patient reported outcome inventory was selected because it is a reliable and clinically meaningful measure of patient reported toxicities and functional outcomes.
Exploratory		

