## **5.0 TREATMENT PLAN**

### **5.1 Study Intervention Description**

Consenting and eligible patients will undergo Lattice SBRT prescribed to a dose of 20 Gy in 5 fractions with a simultaneous integrated boost of 66.7 Gy in 5 fractions. As long as radiotherapy fields do not overlap, treatment of up to 4 other tumor sites are allowed. Lattice SBRT is required for all tumor sites  $\geq 4.5$  cm. Lattice SBRT fractions will be delivered every other day. For sites  $< 4.5$  cm, other planning techniques may be used (i.e. 3D conformal or SBRT). Following radiotherapy, patients will be evaluated for toxicity at 30 days, 3 months, 6 months, and 12 months.

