### **11.3 Data Analysis**

Demographic and clinical characteristics including treatment toxicity will be summarized using descriptive statistics. RECIST 1.1 will be used to determine local control per the protocol described in Appendix E. The RCI will be used to compare the QoL scores between before and after treatment with Lattice SBRT.

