### **RECIST 1.1**

**Target lesions:** The treated lesions (i.e. those defined as treatment targets by the radiation oncologist, GTVs) should be identified as target lesions and recorded and measured at baseline. A sum of the diameters (longest for non-nodal lesions, short axis for nodal lesions) for all target lesions will be calculated and reported as the baseline sum diameters. If lymph nodes are to be included in the sum, then only the short axis is added into the sum. The baseline sum diameters will be used as reference to further characterize any objective tumor regression in the measurable dimension of the disease.

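### The 6-month local-control co-primary is defined for the treated lesion, but Appendix E scores it on a sum over all treated sites, so another site can decide a Lattice lesion's status

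*Combined protocol and SAP*

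**What the plan says.** Three places define or route the endpoint.

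- Section 11.2: "The co-primary endpoints are rate of local control of the treated (i.e. target) lesion at 6 months". It adds: "Local control will be determined by RECIST 1.1 analysis of baseline compared with imaging at 6 months".
- Section 2.0: "Rate of target lesion local control at 6 months per RECIST 1.1".
- Section 11.3: "RECIST 1.1 will be used to determine local control per the protocol described in Appendix E".

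Appendix E sets these rules.

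- **Target lesions:** "The treated lesions (i.e. those defined as treatment targets by the radiation oncologist, GTVs) should be identified as target lesions".
- **Unit:** "A sum of the diameters (longest for non-nodal lesions, short axis for nodal lesions) for all target lesions will be calculated".
- **Progression:** the sum must rise by 20% or more, and by 5 mm or more, over the lowest sum seen during the study, which may be the baseline sum.
- **New lesions:** a note inside the target-lesion definition of progression makes any new lesion progression.

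Section 5.1 says that "treatment of up to 4 other tumor sites are allowed" if fields do not overlap. It requires Lattice for sites of 4.5 cm or more and permits other techniques for smaller ones. Section 5.5 agrees.

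On who is counted, Section 5.8 defines evaluability for toxicity only. Sections 11.2 and 11.4 expect as many as 30% of patients to be unevaluable for local control, because of short survival. The Schedule of Activities notes give the visit window as 180 days +/- 4 weeks, and Section 9.0 makes RECIST forms due at baseline, 3, 6 and 12 months.

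**The concern.** The objective is the efficacy of Lattice SBRT in large lesions. Under the summed rule, a patient's status can be decided by a site that was never given Lattice. Two analysts who follow different sections could then report different co-primary rates from the same scans. The reference for growth raises a similar question in patients with a single lesion, if the tumour shrinks and then regrows.

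No success threshold for local control depends on this. The study's declared purpose, however, is to estimate that rate. With a single arm and no comparator, the definition of control largely determines what the reported figure means.

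**Working it through.** **The plan's own figure.** The 47 evaluable patients reproduce as the smallest n whose worst-case exact (Clopper-Pearson) 95% half-width is at most 0.15: 0.1510 at n = 46 and 0.1493 at n = 47. The 67 enrolled is 47/0.7 = 67.1. Neither number is in dispute.

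**Inputs.** The pilot median treated volume is 435 cc and the evaluable target is 47 (Section 11.2). Up to four other sites are allowed (Section 5.1). Progression needs 20% and 5 mm (Appendix E). Sizes of other sites are assumptions, because the documents give none. Control is taken as not meeting progression; the plan does not spell this out.

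**Lesion versus sum: masking.** As a sphere, 435 cc has diameter (6 x 435/pi)^(1/3) = 9.40 cm. With other sites unchanged, the sum stays below +20% while Lattice growth is below

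(1.2 x total baseline sum - other-site sum)/Lattice diameter - 1,

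which equals 20% + 20% x (other-site sum/Lattice diameter).

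| Lattice lesion | Other sites (assumed, unchanged) | Growth masked up to |
|---|---|---|
| 9.4 cm | one of 1.0 cm | (1.2 x 10.4 - 1.0)/9.4 - 1 = 22.1% |
| 9.4 cm | one of 4.0 cm | (1.2 x 13.4 - 4.0)/9.4 - 1 = 28.5% |
| 9.4 cm | four of 4.0 cm | (1.2 x 25.4 - 16.0)/9.4 - 1 = 54.0% |
| 4.5 cm (entry minimum) | one of 4.0 cm | 20% + 20% x 4.0/4.5 = 37.8% |

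These are examples, not bounds. A second site that shrinks raises the limit. For instance, a Lattice lesion going from 10 to 12.5 cm (+25%) beside a site going from 5 to 3 cm gives a sum of 15 to 15.5 cm (+3.3%), scored as controlled.

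**Lesion versus sum: the reverse.** With the Lattice lesion unchanged at 9.4 cm, a 4.0 cm site that reaches 1.2 x 13.4 - 9.4 = 6.68 cm (+67%) makes the patient progressed.

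**Baseline versus smallest measurement.** A single lesion going 10 to 6 to 8 cm is 8/10 - 1 = -20% from baseline (controlled), but 8/6 - 1 = +33% and +2 cm from the smallest (progressed).

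**Where the passages agree.** For one treated lesion, no new lesion, a 6-month scan and no earlier shrinkage below baseline, every reading gives the same 6-month status.

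**Effect on the rate.** One reclassified patient among 47 is 1/47 = 2.1 points, three are 6.4 and seven are 14.9, against a planned +/- 15.

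**The case without a rule.** Take 35/47 = 74.5% controlled, an illustration inside the 70-85% that Section 11.2 cites for smaller tumours. Counting 1, 3 or 5 documented 3-month failures that lack a 6-month scan gives 35/48 = 72.9%, 35/50 = 70.0% or 35/52 = 67.3%. This calculation adds failures only, so it can move the rate only downward.

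**The case against.** Much of this can be harmonised, and part of that defence stands.

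- **Reference.** Section 11.2 names RECIST 1.1 in the same sentence as baseline. It can be read as naming the scans and leaving the reference to RECIST, whose smallest sum may itself be baseline. A reader might infer two irreconcilable rules; the text supports only an ambiguity.
- **New lesions.** Sections 2.0 and 11.2 speak of the target lesion, and the response table in Appendix E keeps new lesions in a separate column. A target-only reading is natural, though unstated.
- **Unit.** Singular against plural may be loose drafting, and the GTVs in Appendix E could mean Lattice volumes only. No passage says so. Restricting the endpoint to Lattice lesions is itself an inference from the objective. The issue touches only patients with more than one treated site. For them, the literal rule can still give the wrong Lattice status.
- **Evaluability.** A reader might infer that local control has no evaluability rule at all. That goes too far: Section 11.2 requires baseline and 6-month imaging, and the Schedule notes supply the window. What is unwritten is the handling of documented 3-month progression with no 6-month scan.
- **Size.** A reader might treat all 20 unscored patients (67 - 47) as local failures, taking 40/47 = 85.1% to 40/67 = 59.7%. The documents do not support this, because they attribute unevaluability to short survival rather than local progression.

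**Conclusion.** The scoring rule is wrong as written and should be fixed. The firm part is the unit: a literal use of Appendix E lets other treated sites, including non-Lattice ones, decide the status of a Lattice lesion. The reference and the new-lesion clause need clarifying, and one evaluability case needs a rule.

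The per-patient effect is real under the assumed sizes: with one unchanged 4.0 cm site, growth of a 9.4 cm lesion is masked up to about 28%. The effect on the reported rate is 2.1 points per reclassified patient among 47. How many patients are affected, and in which net direction, cannot be determined from the documents. No decision threshold and no sample size changes.

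A reader might also conclude that the primary should become failure by 6 months. The Protocol Summary and Sections 2.0 and 11.2 all specify control at 6 months. Making early failures evaluable, while patients controlled at 3 months without a 6-month scan stay out, would build in a downward shift. That choice belongs in a sensitivity analysis.

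**What to change.** Use one rule in Sections 11.2 and 11.3 and Appendix E.

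1. Score only the Lattice-treated lesion or lesions, each by its own diameter, at the 6-month scan. Local progression is growth of at least 20% and 5 mm from that lesion's smallest measurement on study, which may be baseline.
2. State one patient-level rule for several Lattice lesions, for example failure if any fails.
3. Exclude new and non-Lattice lesions from this endpoint and report them separately.
4. Keep the primary as control at 6 months, with its 95% CI, in patients with a baseline measurement and a scan within 180 days +/- 4 weeks.
5. Report how many patients had documented local progression before 6 months and no 6-month scan, and how many died or were lost without it.
6. Add two sensitivity analyses: (a) count those early progressions as failures, noting that this can only lower the rate; (b) give the 6-month cumulative incidence of local failure in all treated patients, with death as a competing event.

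The cost is wording, plus keeping per-lesion diameters on RECIST forms that are already scheduled. The reported rate may move in either direction. The targets of 47 and 67 stand.

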### **1.6.2 Scientific Rationale for Study Design**

Tumor burden incurs significant morbidity in terms of symptomatology, including pain, dyspnea, hemoptysis, and mass effect on surrounding organs. Palliative hypofractionated radiotherapy is known to be a useful modality for control and/or amelioration of such symptoms. However, large tumors are difficult to treat with traditional palliative methods. Hypofractionated radiotherapy may offer insufficient control and SBRT may be associated with a high rate of toxicity.

Dose escalation using SFRT may offer improved local control, symptom relief, and reduced toxicity compared with traditional radiotherapy methods. Also, SFRT has been associated with significant activation of systemic anti-tumor cytokines and chemokines.

Our initial pilot study of SBRT has been successful thus far, demonstrating that Lattice SBRT is safe and effective treatment for large tumors. However, the pilot study has thus far demonstrated significant heterogeneity in the patient population. Patients are enrolled for different indications and tumor types have varied (i.e. treatment of oligoprogressive disease, palliation of pain, palliation of lung cancer for dyspnea, palliation of sarcoma for bleeding). Further, Lattice SBRT has been followed with varied treatments (i.e. medical therapies, surgery), and sometimes no treatment. Given this heterogeneity, objectively determining the effect of Lattice SBRT both on tumor control and patient QoL is difficult.

This trial of Lattice SBRT will attempt to define efficacy and safety using dual primary endpoints for all patients: local tumor control at 6 months and rate of treatment related grade 3+ CTCAE v5.0 toxicity. Secondary endpoints will then evaluate patient reported QoL in 4 pre-specified sub-groups: sarcomas, thoracic malignancies, gastrointestinal malignancies, and pelvic cancers.

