### **3.2 Exclusion Criteria**

1. Prior high-dose radiotherapy that overlaps with any planned site of protocol radiotherapy. Patients where the Lattice SBRT fields may overlap with the low dose ( $<10$  Gy) region of prior radiotherapy treatments are eligible and may be treated if this is determined to be safe by the treating physician.
2. Patients with tumors in need of urgent surgical intervention, such as life-threatening bleeding or those at high risk for pathologic fracture.
3. Currently receiving any cytotoxic cancer therapy regimens or VEGF inhibitors that will overlap with the Lattice SBRT administration.
  - a. Cytotoxic chemotherapy and VEGF inhibitors prior to radiotherapy or planned after radiotherapy delivery are allowed at the discretion of the treating radiation oncologist. This includes continuing a treatment plan which was initiated prior to the start of radiotherapy. A 2-week washout is recommended, but not required.
4. Pregnant. Women of childbearing potential must have a negative pregnancy test within 20 days of study entry.
5. Patients with HIV are eligible unless their CD4+ T-cell counts are  $< 350$  cells/ $\mu$ L or they have a history of AIDS-defining opportunistic infection within the 12 months prior to registration. Concurrent treatment with effective ART according to DHHS treatment guidelines is recommended. Recommend exclusion of specific ART agents based on predicted drug-drug interactions (i.e. for sensitive CYP3A4 substrates, concurrent strong CYP3A4 inhibitors (ritonavir and cobicistat) or inducers (efavirenz) should be contraindicated).

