## **5.9 Concomitant Therapy and Supportive Care Guidelines**

Patients may not receive any concurrent systemic therapy with radiation. The interval from last receipt of systemic therapy to the initiation (or re-initiation) of systemic therapy will be at physician discretion. Supportive care will be consistent with standards for palliative radiotherapy, directed by the treating physician.

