## Response Criteria

### Evaluation of Target Lesions

**Complete Response (CR):** Disappearance of all target lesions. Any pathological lymph nodes (whether target or non-target) must have reduction in short axis to <10 mm.

**Partial Response (PR):** At least a 30% decrease in the sum of the diameters of target lesions, taking as reference the baseline sum diameters.

**Progressive Disease (PD):** At least a 20% increase in the sum of the diameters of target lesions, taking as reference the smallest sum on study (this includes the baseline sum if that is the smallest on study). In addition to the relative increase of 20%, the sum must also demonstrate an absolute increase of at least 5 mm. (Note: the appearance of one or more new lesions is also considered progressions).

**Stable Disease (SD):** Neither sufficient shrinkage to qualify for PR nor sufficient increase to qualify for PD, taking as reference the smallest sum diameters while on study.

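### Section 11.2 has no rule for scoring 6-month local control when the target lesion is resected, ablated or irradiated again before the scan

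*Combined protocol and SAP*

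**What the plan says.** **Endpoint.** Section 11.2 states: "The co-primary endpoints are rate of local control of the treated (i.e. target) lesion at 6 months". The scoring sentence is: "Local control will be determined by RECIST 1.1 analysis of baseline compared with imaging at 6 months". Section 11.3 refers to Appendix E for the RECIST method. There, complete response for target lesions begins: "Disappearance of all target lesions". Nothing is said about why a lesion has disappeared, and no section lists the RECIST categories that make up local control.

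**Precision.** "Approximately 47 patients would be required to determine local control with a 95% confidence interval of +/- 15" percentage points. Enrollment is set at 67 because "We anticipate that up to 30% of patients may not be evaluable for local control at 6 months". Section 11.2 attributes this loss to short survival. Section 5.8 defines evaluability for toxicity only.

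**Treatment after Lattice SBRT.**
- Systemic therapy: section 3.2 says that cytotoxic chemotherapy and VEGF inhibitors "planned after radiotherapy delivery are allowed at the discretion of the treating radiation oncologist". Section 5.9 says that the interval between systemic treatments "will be at physician discretion".
- Surgery or ablation of the target: not addressed for this trial. On the pilot, section 1.6.2 reports: "Further, Lattice SBRT has been followed with varied treatments (i.e. medical therapies, surgery), and sometimes no treatment". It lists this, together with differing indications and tumor types, as heterogeneity that made the effect on tumor control difficult to determine.
- Further radiotherapy: section 5.5 rules out overlapping Lattice plans during the trial and re-irradiation of sites already irradiated. Both statements stand among the planning instructions.

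**Data capture.** Section 9.0 schedules a RECIST Form at baseline, 3 months, 6 months and 1 year, and a Follow Up Form at each visit. The fields of these forms are not shown.

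**The concern.** The trial has one arm, and section 11.2 says there is no reliable historical comparison. Its main product is therefore the estimated 6-month local control rate. That rate is read from lesion size on two dates, so anything else done to the lesion between those dates is credited to Lattice SBRT unless a rule says otherwise.

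The protocol knows that this can happen, because section 1.6.2 reports it from the pilot. Section 11.2 does name subsequent therapies as a source of heterogeneity, but only for patient-reported outcomes. Nothing equivalent is written for local control.

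The direction matters. A lesion is most likely to be salvaged locally because it has grown. If it is then scored on size at 6 months, or removed from the denominator, a treatment failure disappears from the result. With no written rule, the choice would be made case by case, possibly after the outcomes are known.

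**Working it through.** **1. The plan's own figures.** Section 11.2 does not name the interval method. The exact (Clopper-Pearson) 95% interval at a proportion near 0.5 has a half-width of 0.1510 at n = 46 and 0.1493 at n = 47, so 47 is the smallest n within 0.15. The simple normal formula gives 0.25 × (1.96/0.15)² = 42.7, or 43, and does not match. For enrollment, 47/0.70 = 67.1 and 67 × 0.70 = 46.9. Both 47 and 67 are reproduced, and this point does not alter them.

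**2. Effect per patient.** One lesion scored as controlled instead of failed moves the rate by 1/47 = 2.13 percentage points.

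**3. Three ways to score the same patients.** Let n = 47, let x be the number of lesions controlled on 6-month size, and let k of those x have had local treatment for progression before that scan.
- Scored on size: x/n
- Dropped as non-evaluable: (x − k)/(n − k)
- Counted as failures: (x − k)/n

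For any k between 1 and x − 1, with x below n, the first exceeds the second and the second exceeds the third. Both treatments left open by the silence therefore give a higher rate than counting salvage for progression as failure.

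For illustration, assume x = 38. Then 38/47 = 80.9%, which lies within the 70–85% that section 11.2 quotes from studies of smaller tumors. The values of k are also assumptions, since the documents give none.

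| k | On size | Dropped | Failure |
|---|---|---|---|
| 2 | 80.9% | 36/45 = 80.0% | 36/47 = 76.6% |
| 5 | 80.9% | 33/42 = 78.6% | 33/47 = 70.2% |
| 10 | 80.9% | 28/37 = 75.7% | 28/47 = 59.6% |

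At k = 5, scoring on size is 10.6 points above counting failures, and dropping is still 8.4 points above. At k = 2 the gaps are 4.3 and 3.4 points.

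**4. Procedures not done for progression.** Here failure is the wrong label, and non-evaluable is the natural one. In the same example, five such patients move the rate from 80.9% to 78.6%, or 2.3 points. The reason for the procedure therefore largely determines the size of the effect.

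**The case against.** **Re-irradiation and surgery.** A reader might infer that the plan allows surgery and re-irradiation of the target and credits the result to Lattice SBRT. The documents do not support that. On its face, section 5.5 prohibits re-irradiation. Because it sits in the planning section, it may concern only radiation given before or within protocol treatment, so its reach to later salvage is unclear, but unclear is not allowed. On surgery the documents are silent for this trial, and silence is not permission.

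**Scoring as controlled.** This is a literal reading of the complete-response definition, not a written rule. A resected lesion could equally be called non-evaluable, a category that section 11.2 leaves undefined for local control. Also, Appendix E measures progression from the smallest sum on study and a RECIST Form is due at 3 months, so growth seen then may already be recorded as progression. All of this stands. However, section 11.2 describes a comparison of baseline with 6 months and does not say that earlier progression carries forward. The non-evaluable reading also still biases the rate upward when salvage was for progression.

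**Pilot evidence.** Section 1.6.2 says difficult, not impossible, and cites several kinds of heterogeneity. Later treatment is one of them.

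**Systemic therapy.** Estimating control whatever systemic care follows is a legitimate treatment-policy choice in palliative patients, and section 3.2 foresees continuing a plan begun earlier. This stands in full.

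**Data capture.** Section 9.0 gives form names and schedules only. It cannot be shown that later treatment goes unrecorded.

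**Conclusion.** The gap is real and concerns local treatment of the target lesion. Section 11.2 scores a co-primary endpoint on size at two dates, with no provision for surgery, ablation or further radiotherapy in between. Where such treatment was given for progression, both the literal reading and the non-evaluable reading overstate local control relative to counting the event as failure.

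The firm figure is 2.1 points per patient scored as controlled instead of failed, at 47 evaluable. How many patients would be affected is not in the documents, so the total bias is unknown. A reader might take the five-patient example as evidence of an inflation of 10 points or more. It is only an illustration: it rests on an assumed number of patients and on every procedure having been for progression.

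The sample size is unaffected. Interval systemic therapy is not an error in the plan. The change should be made because the rule is cheap and removes a choice that could otherwise be made after the results are seen.

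**What to change.** Add to section 11.2:

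1. A target lesion counts as not locally controlled if it shows RECIST progression at any scan up to 6 months, or if it receives surgery, ablation or further radiotherapy for progression before the 6-month scan.
2. If a local procedure on the target was not for progression, the patient is not evaluable for local control at 6 months, and the last pre-procedure scan is reported separately.

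This is a scoring rule only. It does not govern whether such treatment may be given, and it works however the re-irradiation statement in section 5.5 is read.

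Confirm that the Follow Up Form records the type, date and reason of any later treatment to the target, and add the fields if it does not. A table of local control with and without interval systemic therapy would be a useful optional description, but it is not a correction.

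**Cost.** Two sentences of endpoint wording and, at most, a few fields at visits already scheduled. The reported rate may be slightly lower, and a few patients may become non-evaluable. Those patients draw on the 30% allowance that section 11.2 attributes to short survival. In the illustration, losing 5 leaves an exact half-width of 13.3 points (33/42) and losing 10 leaves 14.7 (28/37), both within the planned 15. Losing 14 gives 16.1 (24/33).
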